T6402XA, T6402XD, T6402XSToxic effect of aflatoxin, intentional self-harm.T6482XA, T6482XD, T6482XSToxic effect of other mycotoxin food contaminants, intentional self-harm.T650X2A, T650X2D, T650X2SToxic effect of cyanides, intentional self-harm.T651X2A, T651X2D, T651X2SToxic effect of strychnine and its salts, intentional self-harm.T65212A, T65212D, T65212SToxic effect of chewing tobacco, intentional self-harm.T65222A, T6522D, T6522SToxic effect of other tobacco cigarettes, intentional self-harm.T65292A, T65292D, T65292SToxic effect of nitroderivatives and aninoderivatives of benzene and its homologues, intentional self-harm.T653X2A, T653X2D, T653X2SToxic effect of carbon disulfide, intentional self-harm.T654X2A, T654X2D, T654X2SToxic effect of nitroderivatives and aminoderivatives of benzene and its homologues, intentional self-harm.T655X2A, T655X2D, T655X2SToxic effect of nitroglycerin and other nitric acids and esters, intentional self-harm.T656X2A, T656X2D, T65812SToxic effect of paints and dyes, not elsewhere classified, intentional self-harm.T65812A, T65812D, T65812SToxic effect of latex, intentional self-harm.T65822A, T65822D, T65822SToxic effect of harmful algae and algae toxins, intentional self- harm.T65832A, T65832D, T65832SToxic effect of fiberglass, intentional self-harm.	T6392XA, T6392XD, T6392XS	Toxic effect of contact with unspecified venomous animal, intentional self-harm.
T6482XA, T6482XD, T6482XSToxic effect of other mycotoxin food contaminants, intentional self-harm.T650X2A, T650X2D, T650X2SToxic effect of cyanides, intentional self-harm.T651X2A, T651X2D, T651X2SToxic effect of strychnine and its salts, intentional self-harm.T65212A, T65212D, T65212SToxic effect of chewing tobacco, intentional self-harm.T65222A, T65222D, T65222SToxic effect of tobacco cigarettes, intentional self-harm.T65292A, T65292D, T65292SToxic effect of other tobacco and nicotine, intentional self-harm.T653X2A, T653X2D, T653X2SToxic effect of nitroderivatives and aminoderivatives of benzene and its homologues, intentional self-harm.T654X2A, T654X2D, T654X2SToxic effect of nitroglycerin and other nitric acids and esters, intentional self-harm.T655X2A, T655X2D, T655X2SToxic effect of paints and dyes, not elsewhere classified, intentional self-harm.T65812A, T65812D, T65812SToxic effect of latex, intentional self-harm.T65822A, T65822D, T65822SToxic effect of harmful algae and algae toxins, intentional self-harm.T65832A, T65832D, T65832SToxic effect of fiberglass, intentional self-harm.	T6402XA, T6402XD, T6402XS	Toxic effect of aflatoxin, intentional self-harm.
T650X2A, T650X2D, T650X2SToxic effect of cyanides, intentional self-harm.T651X2A, T651X2D, T651X2SToxic effect of strychnine and its salts, intentional self-harm.T65212A, T65212D, T65212SToxic effect of chewing tobacco, intentional self-harm.T65222A, T65222D, T65222SToxic effect of tobacco cigarettes, intentional self-harm.T65292A, T65292D, T65292SToxic effect of other tobacco and nicotine, intentional self-harm.T653X2A, T653X2D, T653X2SToxic effect of nitroderivatives and aminoderivatives of benzene and its homologues, intentional self-harm.T654X2A, T654X2D, T654X2SToxic effect of nitroglycerin and other nitric acids and esters, intentional self-harm.T655X2A, T655X2D, T655X2SToxic effect of paints and dyes, not elsewhere classified, intentional self-harm.T65812A, T65812D, T65812SToxic effect of latex, intentional self-harm.T65822A, T65822D, T65822SToxic effect of latex, intentional self-harm.T65822A, T65822D, T6582SToxic effect of paints and dyes, not elsewhere classified, intentional self-harm.T65822A, T65822D, T6582SToxic effect of latex, intentional self-harm.T65822A, T65822D, T6582SToxic effect of latex, intentional self-harm.T65822A, T65822D, T6582SToxic effect of latex, intentional self-harm.T65832A, T65832D, T65832SToxic effect of harmful algae and algae toxins, intentional self-harm.	T6482XA, T6482XD, T6482XS	Toxic effect of other mycotoxin food contaminants, intentional self-harm.
T651X2A, T651X2D, T651X2SToxic effect of strychnine and its salts, intentional self-harm.T65212A, T65212D, T65212SToxic effect of chewing tobacco, intentional self-harm.T65222A, T65222D, T65222SToxic effect of tobacco cigarettes, intentional self-harm.T65292A, T65292D, T65292SToxic effect of other tobacco and nicotine, intentional self-harm.T653X2A, T653X2D, T653X2SToxic effect of nitroderivatives and aminoderivatives of benzene and its homologues, intentional self-harm.T654X2A, T654X2D, T654X2SToxic effect of carbon disulfide, intentional self-harm.T655X2A, T655X2D, T655X2SToxic effect of nitroglycerin and other nitric acids and esters, intentional self-harm.T656X2A, T656X2D, T656X2SToxic effect of paints and dyes, not elsewhere classified, intentional self-harm.T65812A, T65812D, T65812SToxic effect of latex, intentional self-harm.T65822A, T65822D, T65822SToxic effect of harmful algae and algae toxins, intentional self-harm.T65832A, T65832D, T65832SToxic effect of fiberglass, intentional self-harm.	T650X2A, T650X2D, T650X2S	Toxic effect of cyanides, intentional self-harm.
T65212A, T65212D, T65212SToxic effect of chewing tobacco, intentional self-harm.T65222A, T65222D, T65222SToxic effect of tobacco cigarettes, intentional self-harm.T65292A, T65292D, T65292SToxic effect of other tobacco and nicotine, intentional self-harm.T653X2A, T653X2D, T653X2SToxic effect of nitroderivatives and aminoderivatives of benzene and its homologues, intentional self-harm.T654X2A, T654X2D, T654X2SToxic effect of carbon disulfide, intentional self-harm.T655X2A, T655X2D, T655X2SToxic effect of nitroglycerin and other nitric acids and esters, intentional self-harm.T656X2A, T656X2D, T656X2SToxic effect of paints and dyes, not elsewhere classified, intentional self-harm.T65812A, T65812D, T65812SToxic effect of latex, intentional self-harm.T65822A, T65822D, T65822SToxic effect of harmful algae and algae toxins, intentional self-harm.T65832A, T65832D, T65832SToxic effect of fiberglass, intentional self-harm.	T651X2A, T651X2D, T651X2S	Toxic effect of strychnine and its salts, intentional self-harm.
T65222A, T65222D, T65222SToxic effect of tobacco cigarettes, intentional self-harm.T65292A, T65292D, T65292SToxic effect of other tobacco and nicotine, intentional self-harm.T653X2A, T653X2D, T653X2SToxic effect of nitroderivatives and aminoderivatives of benzene and its homologues, intentional self-harm.T654X2A, T654X2D, T654X2SToxic effect of carbon disulfide, intentional self-harm.T655X2A, T655X2D, T655X2SToxic effect of nitroglycerin and other nitric acids and esters, intentional self-harm.T656X2A, T656X2D, T656X2SToxic effect of paints and dyes, not elsewhere classified, intentional self-harm.T65812A, T65812D, T65812SToxic effect of latex, intentional self-harm.T65822A, T65822D, T65822SToxic effect of harmful algae and algae toxins, intentional self-harm.T65832A, T65832D, T65832SToxic effect of fiberglass, intentional self-harm.	T65212A, T65212D, T65212S	Toxic effect of chewing tobacco, intentional self-harm.
T65292A, T65292D, T65292SToxic effect of other tobacco and nicotine, intentional self- harm.T653X2A, T653X2D, T653X2SToxic effect of nitroderivatives and aminoderivatives of benzene and its homologues, intentional self-harm.T654X2A, T654X2D, T654X2SToxic effect of carbon disulfide, intentional self-harm.T655X2A, T655X2D, T655X2SToxic effect of nitroglycerin and other nitric acids and esters, intentional self-harm.T656X2A, T656X2D, T655X2SToxic effect of paints and dyes, not elsewhere classified, intentional self-harm.T65812A, T65812D, T65812SToxic effect of latex, intentional self-harm.T65822A, T65822D, T65822SToxic effect of harmful algae and algae toxins, intentional self- harm.T65832A, T65832D, T65832SToxic effect of fiberglass, intentional self-harm.	T65222A, T65222D, T65222S	Toxic effect of tobacco cigarettes, intentional self-harm.
T653X2A, T653X2D, T653X2SToxic effect of nitroderivatives and aminoderivatives of benzene and its homologues, intentional self-harm.T654X2A, T654X2D, T654X2SToxic effect of carbon disulfide, intentional self-harm.T655X2A, T655X2D, T655X2SToxic effect of nitroglycerin and other nitric acids and esters, intentional self-harm.T656X2A, T656X2D, T656X2SToxic effect of paints and dyes, not elsewhere classified, intentional self-harm.T65812A, T65812D, T65812SToxic effect of latex, intentional self-harm.T65822A, T65822D, T65822SToxic effect of harmful algae and algae toxins, intentional self-harm.T65832A, T65832D, T65832SToxic effect of fiberglass, intentional self-harm.	T65292A, T65292D, T65292S	Toxic effect of other tobacco and nicotine, intentional self-harm.
T654X2A, T654X2D, T654X2SToxic effect of carbon disulfide, intentional self-harm.T655X2A, T655X2D, T655X2SToxic effect of nitroglycerin and other nitric acids and esters, intentional self-harm.T656X2A, T656X2D, T656X2SToxic effect of paints and dyes, not elsewhere classified, intentional self-harm.T65812A, T65812D, T65812SToxic effect of latex, intentional self-harm.T65822A, T65822D, T65822SToxic effect of harmful algae and algae toxins, intentional self- harm.T65832A, T65832D, T65832SToxic effect of fiberglass, intentional self-harm.	T653X2A, T653X2D, T653X2S	Toxic effect of nitroderivatives and aminoderivatives of benzene and its homologues, intentional self-harm.
T655X2A, T655X2D, T655X2SToxic effect of nitroglycerin and other nitric acids and esters, intentional self-harm.T656X2A, T656X2D, T656X2SToxic effect of paints and dyes, not elsewhere classified, intentional self-harm.T65812A, T65812D, T65812SToxic effect of latex, intentional self-harm.T65822A, T65822D, T65822SToxic effect of harmful algae and algae toxins, intentional self- harm.T65832A, T65832D, T65832SToxic effect of fiberglass, intentional self-harm.	T654X2A, T654X2D, T654X2S	Toxic effect of carbon disulfide, intentional self-harm.
T656X2A, T656X2D, T656X2SToxic effect of paints and dyes, not elsewhere classified, intentional self-harm.T65812A, T65812D, T65812SToxic effect of latex, intentional self-harm.T65822A, T65822D, T65822SToxic effect of harmful algae and algae toxins, intentional self- harm.T65832A, T65832D, T65832SToxic effect of fiberglass, intentional self-harm.	T655X2A, T655X2D, T655X2S	Toxic effect of nitroglycerin and other nitric acids and esters, intentional self-harm.
T65812A, T65812D, T65812SToxic effect of latex, intentional self-harm.T65822A, T65822D, T65822SToxic effect of harmful algae and algae toxins, intentional self-harm.T65832A, T65832D, T65832SToxic effect of fiberglass, intentional self-harm.	T656X2A, T656X2D, T656X2S	Toxic effect of paints and dyes, not elsewhere classified, intentional self-harm.
T65822A, T65822D, T65822SToxic effect of harmful algae and algae toxins, intentional self- harm.T65832A, T65832D, T65832SToxic effect of fiberglass, intentional self-harm.	T65812A, T65812D, T65812S	Toxic effect of latex, intentional self-harm.
T65832A, T65832D, T65832SToxic effect of fiberglass, intentional self-harm.	T65822A, T65822D, T65822S	Toxic effect of harmful algae and algae toxins, intentional self- harm.
	T65832A, T65832D, T65832S	Toxic effect of fiberglass, intentional self-harm.

Toxic Effects	
T65892A, T65892D, T65892S	Toxic effect of other specified substances, intentional self-harm.
T6592XA, T6592XD, T6592XS	Toxic effect of unspecified substance, intentional self-harm.

Asphyxiation:	
T71112A, T71112D, T71112S	Asphyxiation due to smothering under pillow, intentional self-
	harm.
T71122A, T71122D, T71122S	Asphyxiation due to plastic bag, intentional self-harm.
T71132A, T71132D, T71132S	Asphyxiation due to being trapped in bed linens, intentional
	self-harm.
T71152A, T71152D, T71152S	Asphyxiation due to smothering in furniture, intentional self-
	harm.
T71162A, T71162D, T71162S	Asphyxiation due to hanging, intentional self-harm.
T71192A, T71192D, T71192S	Asphyxiation due to mechanical threat to breathing due to other
	causes, intentional self-harm.
T71222A, T71222D, T71222S	Asphyxiation due to being trapped in a car trunk, intentional
	self-harm.
T71232A, T71232D, T71232S	Asphyxiation due to being trapped in a (discarded) refrigerator,
	intentional self-harm.

* Note: Please note that all codes end in either A, D or S. These codes refer to (A) Initial Encounter, (D) Subsequent Encounter, or (S) Sequela.

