4.1.4. Outcomes

The primary outcome measure will be a composite of the incidence of suicides and/or re-presentations to any Emergency Department in Ontario for self-harm in the year after the index episode of self-harm. The incidence of suicide and re-representation to Emergency Department will be measured using ICD-10-CM codes T360-T50992, T510-T6592, T71112-T71232, X71-X83 (refer to Appendix A for full list of codes and descriptors) [46]. Individuals who died by suicide will be identified in ICES using the Vital Statistics - Death Database. A potential problem with the outcome measures in this trial is that the intervention may also change help-seeking behaviour. That is, men may seek out healthcare that they would not have in the past, which may lead to an increase in re-presentations to the Emergency Department for patients in the intervention group. In order to explore changes to health-related help-seeking, we will also collect data on primary care and hospital outpatient care not driven by emergencies through ICES. This will be measured in ICES, using the Ontario Health Insurance Plan (OHIP) Claims Database and National Ambulatory Care Reporting System Metadata (NACRS). We will also address this through a sub-study of smartphone-assisted PST.

The secondary outcome measures will include total number of suicides; representations to any Emergency Department in Ontario for the repetition of self-harm; representations to any Emergency Department in Ontario for any reason; other health system use including use of primary care and hospital outpatient appointments; mortality not related to suicide; and, health system costs within one year which will inform an economic analysis. All outcomes will be identified and measured using routinely collected data housed at ICES. Men who present with intentional self-harm in the study Emergency Departments will be identified from ICES administrative health data.

	Justification	Data Source	Data Collection Period
Primary Outcome Va	riable (composite outco	ome variable)	
Death by Suicide	To assess the clinical	ORGD, NACRS	Baseline; 12 months
and/or re-	impact of the	(ICES)	
presentation to any	provision of a		
Emergency	smartphone-assisted		
Department in	PST service.		
Ontario for Self-harm			
Secondary Outcomes	Secondary Outcomes		
Death by Suicide	To assess the clinical	ORGD (ICES)	Baseline; 12 months
	impact of the		
	provision of a		
	smartphone-assisted		
	PST service.		

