6.2. Appendix B – ICD-10-CM Self-Harm Codes Included in Collection

Code*	Description
Self-Injury	
X710XXA, X710XXD,	Intentional self-harm by drowning or submersion while in
X710XXS	bathtub.
X711XXA, X711XXD,	Intentional self-harm by drowning or submersion while in
X711XXS	swimming pool.
X712XXA, X712XXD,	Intentional self-harm by drowning or submersion after
X712XXS	jump into swimming pool.
Self-Injury	
X713XXA, X713XXD,	Intentional self-harm by drowning and submersion in
X713XXS	natural water.
X718XXA, X718XXD,	Other intentional self-harm by drowning or submersion
X718XXS	Other mentional sen-nami by drowning of submersion.
X719XXA, X719XXD,	Intentional self-harm by drowning or submersion,
X719XXS	unspecified.
X72XXXA, X72XXXD,	Intentional self-harm by handoun discharge
X72XXXS	intentional sent narm by nanogan disenarge.
X730XXA, X730XXD,	Intentional self-harm by shotgun discharge
X730XXS	intentional sent narm by shotgan alsonarge.
X731XXA, X731XXD,	Intentional self-harm by hunting rifle discharge
X731XXS	intentional ben nami og namming mile albenarge.
X732XXA, X732XXD,	Intentional self-harm by machine-gun discharge
X732XXS	intentional ben name by machine gan albenaige.
X738XXA, X738XXD,	Intentional self-harm by other larger firearm discharge
X738XXS	
X739XXA, X739XXD,	Intentional self-harm by unspecified larger firearm
X739XXS	discharge.
X7401XA X7401XD	
X7401XS	Intentional self-harm by airgun.
X7402XA X7402XD	
Λ/402ΛΑ, Λ/402ΛD, V7402VS	Intentional self-harm by paintball gun.
A/402AD	

Self-Injury	
X7409XA, X7409XD,	Intentional self-harm by other gas, air or spring operated
X7409XS	gun.
X748XXA, X748XXD,	Intentional calf harm by other firearm discharge
X748XXS	intentional sen-narm by other meanin discharge.
X749XXA, X749XXD,	Intentional calf harm by unanacified firearm discharge
X749XXS	intentional sen-narm by unspecified meanin discharge.
X75XXXA, X75XXXD,	Intentional salf harm by avalagive material
X75XXXS	intentional sen-narm by explosive material.
X76XXXA, X76XXXD,	Intentional salf harm by smales, fire and flamos
X76XXXS	intentional sen-nami by smoke, me and mames.
X770XXA, X770XXD,	Intentional self harm by steam or bot vanours
X770XXS	intentional sen-narm by steam of not vapours.
X771XXA, X771XXD,	Intentional self-harm by hot tan water
X771XXS	intentional sem-narm by not tap water.
X772XXA, X772XXD,	Intentional self-harm by other hot fluids
X772XXS	intentional ben nami by other not nards.

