T422X2A, T422X2D, T422X2S	Poisoning by succinimides and oxazolidinediones, intentional self-harm.
T423X2A, T423X2D, T423X28	Poisoning by barbiturates, intentional self-harm.
T424X2A, T424X2D, T424X2S	Poisoning by benzodiazepines, intentional self-harm.

Poisoning:	
T425X2A, T425X2D, T425X2S	Poisoning by mixed antiepileptics, intentional self-harm.
T426X2A, T426X2D, T426X2S	Poisoning by other antiepileptic and sedative-hypnotic drugs, intentional self-harm.
T428X2A, T428X2D, T428X2S	Poisoning by antiparkinsonism drugs and other central muscle- tone depressants, intentional self-harm.
T43012A, T43012D, T43012S	Poisoning by tricyclic antidepressants, intentional self-harm.
T431X2A, T431X2D, T431X2S	Poisoning by monoamine-oxidase-inhibitor antidepressants, intentional self-harm.
T43202A, T43202D, T43202S	Poisoning by unspecified antidepressants, intentional self-harm.
T43212A, T43212D, T43212S	Poisoning by selective serotonin and norepinephrine reuptake inhibitors, intentional self-harm.
T43222A, T43222D, T432228	Poisoning by selective serotonin reuptake inhibitors, intentional self-harm.
T43292A, T43292D, T43292S	Poisoning by other antidepressants, intentional self-harm.
T433X2A, T433X2D, T433X2S	Poisoning by phenothiazine antipsychotics and neuroleptics, intentional self-harm.
T434X2A, T434X2D, T434X2S	Poisoning by butyrophenone and thiothixene neuroleptics, intentional self-harm.
T43502A, T43502D, T43502S	Poisoning by unspecified antipsychotics and neuroleptics, intentional self-harm.
T43592A, T43592D, T43592S	Poisoning by other antipsychotics and neuroleptics, intentional self-harm.
T43602A, T43602D, T43602S	Poisoning by unspecified psychostimulants, intentional self- harm.
T43612A, T43612D, T43612S	Poisoning by caffeine, intentional self-harm.
T43622A, T43622D, T43622S	Poisoning by amphetamines, intentional self-harm.
T43632A, T43632D, T43632S	Poisoning by methylphenidate, intentional self-harm.
T43692A, T43692D, T43692S	Poisoning by other psychostimulants, intentional self-harm.
1438X2A, 1438X2D, 1438X2S	Poisoning by other psychotropic drugs, intentional self-harm.
T4392XA, T4392XD, T4392XS	Poisoning by unspecified psychotropic drug, intentional self- harm.
T440X2A, T440X2D, T440X2S	Poisoning by anticholinesterase agents, intentional self-harm.
T441X2A, T441X2D, T441X2S	Poisoning by other parasympathomimetics [cholinergics], intentional self-harm.
T442X2A, T442X2D, T442X2S	Poisoning by ganglionic blocking drugs, intentional self-harm.

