T443X2A, T443X2D, T443X2S	Poisoning by other parasympatholytics [anticholinergics and antimuscarinics] and spasmolytics, intentional self-harm.
T444X2A, T444X2D, T444X2S	Poisoning by predominantly alpha-adrenoreceptor agonists, intentional self-harm.
T446X2A, T446X2D, T446X2S	Poisoning by alpha-adrenoreceptor antagonists, intentional self-harm.
T447X2A, T447X2D, T447X2S	Poisoning by beta-adrenoreceptor antagonists, intentional self- harm.
T448X2A, T448X2D, T448X2S	Poisoning by centrally-acting and adrenergic-neuron-blocking agents, intentional self-harm.
T44902A, T44902D, T44902S	Poisoning by unspecified drugs primarily affecting the autonomic nervous system, intentional self-harm.
T450X2A, T450X2D, T450X2S	Poisoning by antiallergic and antiemetic drugs, intentional self- harm.

Poisoning:	
T451X2A, T451X2D, T451X2S	Poisoning by antineoplastic and immunosuppressive drugs, intentional self-harm.
T452X2A, T452X2D, T452X2S	Poisoning by vitamins, intentional self-harm.
T453X2A, T453X2D, T453X2S	Poisoning by enzymes, intentional self-harm.
T454X2A, T454X2D, T454X2S	Poisoning by iron and its compounds, intentional self-harm.
T45512A, T45512D, T45512S	Poisoning by anticoagulants, intentional self-harm.
T45522A, T45522D, T45522S	Poisoning by antithrombotic drugs, intentional self-harm.
T45602A, T45602D, T45602S	Poisoning by unspecified fibrinolysis-affecting drugs, intentional self-harm.
T45612A, T45612D, T45612S	Poisoning by thrombolytic drug, intentional self-harm.
T45622A, T45622D, T45622S	Poisoning by hemostatic drug, intentional self-harm.
T45692A, T45692D, T45692S	Poisoning by other fibrinolysis-affecting drugs, intentional self- harm.
T457X2A, T457X2D, T457X2S	Poisoning by anticoagulant antagonists, vitamin K and other coagulants, intentional self-harm.
T458X2A, T458X2D, T458X2S	Poisoning by other primarily systemic and hematological agents, intentional self-harm.
T460X2A, T460X2D, T460X2S	Poisoning by cardiac-stimulant glycosides and drugs of similar action, intentional self-harm.
T461X2A, T461X2D, T461X2S	Poisoning by calcium-channel blockers, intentional self-harm.
T462X2A, T462X2D, T462X2S	Poisoning by other antidysrhythmic drugs, intentional self- harm.
T463X2A, T463X2D, T463X2S	Poisoning by coronary vasodilators, intentional self-harm.
T464X2A, T464X2D, T464X2S	Poisoning by angiotensin-converting-enzyme inhibitors, intentional self-harm.
T465X2A, T465X2D, T465X2S	Poisoning by other antihypertensive drugs, intentional self- harm.

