T491X2A, T491X2D, T491X2S	Poisoning by antipruritics, intentional self-harm.
T492X2A, T492X2D, T492X2S	Poisoning by local astringents and local detergents, intentional self-harm.
T493X2A, T493X2D, T493X2S	Poisoning by emollients, demulcents and protectants, intentional self-harm.
T494X2A, T494X2D, T494X2S	Poisoning by keratolytics, keratoplastics, and other hair treatment drugs, intentional self-harm.
T495X2A, T495X2D, T495X2S	Poisoning by ophthalmological drugs and preparations, intentional self-harm.
T496X2A, T496X2D, T496X2S	Poisoning by otorhinolaryngological drugs and preparations, intentional self-harm.
T497X2A, T497X2D, T497X2S	Poisoning by dental drugs, topically applied, intentional self- harm.
T498X2A, T498X2D, T498X2S	Poisoning by other topical agents, intentional self-harm.
T4992XA, T4992XD, T4992XS	Poisoning by unspecified topical agent, intentional self-harm.
T500X2A, T500X2D, T500X2S	Poisoning by mineralocorticoids and their antagonists, intentional self-harm.
T501X2A, T501X2D, T501X2S	Poisoning by loop [high-ceiling] diuretics, intentional self- harm.
T501X2A, T501X2D, T501X2S	Poisoning by carbonic-anhydrase inhibitors, benzothiadiazides and other diuretics, intentional self-harm.
T503X2A, T503X2D, T503X2S	Poisoning by electrolytic, caloric and water-balance agents, intentional self-harm.
T504X2A, T504X2D, T504X2S	Poisoning by drugs affecting uric acid metabolism, intentional self-harm.
T505X2A, T505X2D, T505X2S	Poisoning by appetite depressants, intentional self-harm.
T506X2A, T506X2D, T506X2S	Poisoning by antidotes and chelating agents, intentional self- harm.
T507X2A, T507X2D, T507X2S	Poisoning by analeptics and opioid receptor antagonists, intentional self-harm.

Poisoning:	
T508X2A, T508X2D, T508X2S	Poisoning by diagnostic agents, intentional self-harm.
T50A12A T50A12D T50A12S	Poisoning by pertussis vaccine, including combinations with a
130A12A, 130A12D, 130A125	pertussis component, intentional self-harm.
T50A22A, T50A22D, T50A22S	Poisoning by mixed bacterial vaccines, intentional self-harm.
T50A92A, T50A92D, T50A92S	Poisoning by other bacterial vaccines, intentional self-harm.
T50B12A, T50B12D, T50B12S	Poisoning by smallpox vaccines, intentional self-harm.
T50B92A, T50B92D, T50B92S	Poisoning by other viral vaccines, intentional self-harm.
T50Z12A, T50Z12D, T50Z12S	Poisoning by immunoglobulin, intentional self-harm.
T50Z92A, T50Z92D, T50Z92S	Poisoning by other vaccines and biological substances,
	intentional self-harm.

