T50002A T50002D T50002S	Poisoning by unspecified drugs medicaments, and biological
150902A, 150902D, 150902S	substances, intentional self-harm.
T50002A T50002D T50002S	Poisoning by other drugs, medicaments and biological
150392A, 150792D, 1509925	substances, intentional self-harm.

Toxic Effects	
T510X2A, T510X2D, T510X2S	Toxic effect of ethanol, intentional self-harm.
T511X2A, T511X2D, T511X2S	Toxic effect of methanol, intentional self-harm.
T512X2A, T512X2D, T512X2S	Toxic effect of 2-Propanol, intentional self-harm.
T513X2A, T513X2D, T513X2S	Toxic effect of fusel oil, intentional self-harm.
T518X2A, T518X2D, T518X2S	Toxic effect of other alcohols, intentional self-harm.
T519X2A, T519X2D, T519X2S	Toxic effect of unspecified alcohol, intentional self-harm.
T520X2A, T520X2D, T520X2S	Toxic effect of petroleum products, intentional self-harm.
T521X2A, T521X2D, T521X2S	Toxic effect of benzene, intentional self-harm.
T522X2A, T522X2D, T522X2S	Toxic effect of homologues of benzene, intentional self-harm.
T523X2A, T523X2D, T523X2S	Toxic effect of glycols, intentional self-harm.
T524X2A, T524X2D, T524X2S	Toxic effect of ketones, intentional self-harm.
T528X2A, T528X2D, T528X2S	Toxic effect of other organic solvents, intentional self-harm.
T5292XA T5292XD T5292XS	Toxic effect of unspecified organic solvents, intentional self-
,,,,,	harm.
T530X2A, T530X2D, T530X2S	Toxic effect of carbon tetrachloride, intentional self-harm.
T531X2A, T531X2D, T531X2S	Toxic effect of chloroform, intentional self-harm.
T532X2A, T532X2D, T532X2S	Toxic effect of trichloroethylene, intentional self-harm.
T534X2A, T534X2D, T534X2S	Toxic effect of dichloromethane, intentional self-harm.
T535X2A, T535X2D, T535X2S	Toxic chlorofluorocarbons, intentional self-harm.
T536X2A T536X2D T536X2S	Toxic effect of other halogen derivative of aliphatic
1550121, 1550120, 1550125	hydrocarbons, intentional self-harm.
T527Y2A T527Y2D T527Y2S	Toxic effect of other halogen derivative of aromatic
1557A2A, 1557A2D, 1557A2S	hydrocarbons, intentional self-harm.
T5392XA, T5392XD, T5392XS	Toxic effect of unspecified halogen derivative of aliphatic and
	aromatic hydrocarbons, intentional self-harm.
T540X2A, T540X2D, T540X2S	Toxic effect of phenol and phenol homologues, intentional self- harm.
	Toxic effect of other corrosive organic compounds, intentional
T541X2A, T541X2D, T541X2S	self-harm.
TSADYDA TSADYDD TSADYDS	Toxic effect of corrosive acids and acid-like substances,

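### Appendix B prints one code for two diuretic classes and has no T502 row, so the code list and the ranges in section 4.1.4 define different self-harm re-presentation outcomes

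*Protocol*

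**What the plan says.** The primary outcome is suicide and/or an Emergency Department re-presentation for self-harm within a year of the index episode. All outcomes come from routine data held at ICES. Section 4.1.4 says the events are "measured using ICD-10-CM codes T360-T50992, T510-T6592, T71112-T71232, X71-X83 (refer to Appendix A for full list of codes and descriptors".

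The list itself is headed "6.2. Appendix B – ICD-10-CM Self-Harm Codes Included in Collection". Section 4.1.1 describes Appendix A as the list of sites.

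Within Appendix B:

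- The row "Poisoning by loop [high-ceiling] diuretics, intentional self- harm" is coded T501X2A/D/S.
- The row directly below it, "Poisoning by carbonic-anhydrase inhibitors, benzothiadiazides and other diuretics, intentional self-harm", is also coded T501X2A/D/S.
- The row after that is T503X2A/D/S. No row carries T502.
- T426 is followed by "T428X2A, T428X2D, T428X2S".
- T444 is followed by "T446X2A, T446X2D, T446X2S".
- T532 is followed by "T534X2A, T534X2D, T534X2S".

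**The concern.** The trial plans no participant contact for outcome collection, so the code set is in practice the definition of a re-presentation. The protocol gives that code set twice, as ranges and as an itemised list, and the two do not match. A programmer working from the ranges and one working from the list would pull different records. Under the list, a man whose only qualifying re-presentation carried T502 would be scored event-free. Under the ranges he would count.

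The ranges cannot simply replace the list. As written they name whole blocks of poisoning and toxic-effect codes, while the T-code rows of Appendix B are confined to intentional self-harm. The list carries a restriction that the ranges do not state, so it has to be right. Section 3.1.1 puts ingestions at about 80% of Emergency Department self-harm episodes, so the poisoning block is not peripheral, although the affected classes may be only a small part of it.

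**Working it through.** The plan states no figure on this point, so the check compares the two statements of the code set.

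**1. The duplicate.** The T50 rows run T500, T501, T501, T503, T504 and so on. One number is used twice and one is missing. The second T501 row names a different drug class from the first. All three suffixes (A, D, S) repeat cleanly and the neighbouring rows are intact, so this is not a fault of reading the PDF. T502 lies inside T360-T50992. This discrepancy is established from the protocol alone.

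**2. Other skipped numbers inside the ranges.** Listing the four-character stems block by block shows these gaps between cleanly read rows:

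- T427, between T426 and T428. The T42 block also has no closing row for unspecified agents, unlike most blocks.
- T445, between T444 (alpha agonists) and T446 (alpha antagonists), within a run of adrenergic classes.
- T533, between two named solvents.

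A skipped number does not show that a category exists. The list has many other jumps, such as T375 to T378, T394 to T398, T436 to T438, T513 to T518 and T537 to T539, and these may simply be unused numbers. Telling the two apart needs the classification, which is not at hand.

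**3. Unpaired rows.** Some blocks print an unspecified row and an other row together (T40902/T40992, T46902/T46992, T48902/T48992). T38902, T44902 and T48202 stand alone. This is an inference from pattern and also needs checking.

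**4. Rows not used.** The rows that appear as T50002 and the scrambled rows late in the toxic-effects block are reading faults and are not evidence.

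**5. Possible size.** The documents give no code frequencies. Suppose a share s of events is missed equally in both arms.

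- Relative reduction: 1 − [0.065(1−s)] / [0.13(1−s)] = 50% for any s, so it does not change.
- Power, from the inputs in section 4.1.5 (mean cluster size 80, coefficient of variation 0.30, ICC 0.01, 10 and 15 clusters): the design effect for a post-period comparison is 1 + [(0.30² + 1) × 80 − 1] × 0.01 = 1.862. The effective sizes are 1,200/1.862 = 644 control and 800/1.862 = 430 intervention.
- With power = Φ[(Δ − 1.96·SE₀)/SE₁], where SE₀ is pooled and SE₁ unpooled, 13% versus 6.5% gives 94.0%. The same method gives 79.2% for 13% versus 7.7%, against the protocol's 80%.
- With s = 5%, an assumed and deliberately generous value, the rates become 12.35% and 6.175% and power is 92.7%. Using the inter-period correlation of 0.008, the corresponding falls are 96.5% to 95.6% (baseline-adjusted) and 87.0% to 85.0% (pre-post difference).

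**The case against.** The strongest reply is that section 4.1.4 says events are measured by the ranges, which contain T502. The appendix would then only illustrate, and the descriptor shows which class was meant. In part this stands. It would be too strong to say that Appendix B alone decides who has a primary event: the text gives ranges, points to a different appendix, and identifies suicides through the death database. What remains is that the same sentence calls the appendix list complete, the list alone carries the restriction to intentional self-harm, and nothing says which governs.

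A reader might also infer that at least four categories are missing, plus several rows for other agents. The document does not support that. Only T502 is shown, because its class is named under another code. The remaining gaps are candidates.

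Finally, the consequence is slight. No frequencies are given, any assumed share of lost events is a guess, and nothing suggests that the loss would differ between arms. The 80% ingestion figure describes all Emergency Department self-harm episodes, not re-presentations in this male cohort, so it does not size the loss. This part of the objection stands, and it sets the weight of the point.

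**Conclusion.** The point holds as a minor correction. The list assigns one code to two drug classes and omits T502, which the ranges include, so the re-presentation component of the primary outcome has two non-identical definitions. T427, T445, T533 and the unpaired rows at T38902, T44902 and T48202 should be checked. The reference to Appendix A is wrong.

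The likely effect is small. Assuming equal loss in both arms, the relative reduction is unchanged, and even an assumed 5% loss of events costs about 1 to 2 points of power. The documents do not show bias between arms or a failure of power, and neither should be inferred. The reason to act is reproducibility: the primary outcome should have one code set, fixed before data are extracted.

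A separate mismatch should not be folded into this one. Section 4.1.2 identifies index episodes by T14.91 and X71-X83, which is a different code set from that in section 4.1.4.

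**What to change.** Before the ICES cohort is cut:

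1. Correct the second T501 row to the code of the class it describes.
2. Check Appendix B by program against the classification over the ranges in section 4.1.4, restricted to intentional self-harm. Add any category found missing. Where a skipped number is unused, no change is needed.
3. Change the reference in section 4.1.4 from Appendix A to Appendix B.
4. State that the corrected list governs the self-harm re-presentation outcome.

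Reconcile the index-episode codes in section 4.1.2 as a separate item. The corrected outcome list should not silently redefine eligibility.

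The cost is about an hour of code-list work and a short amendment. No sample-size or power figure in the protocol changes.
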